5.2 Drug/Device Handling

Indocyanine green (ICG) used in this study will be ordered from the investigational pharmacy and supplied through the usual pharmacy dispensing mechanisms.

ICG is FDA approved for routine clinical practice and is currently available through the investigational pharmacy at DHMC. The results of this study are not intended to produce a new indication for the drug and will not be reported to the FDA. Nor will the results of this study significantly change the way that the drug is marketed in the United States. The medication will be utilized for an indication, and in a clinical setting, where it is currently utilized as part of usual care at this institution. ICG is lawfully marketed in the United States. The research will be conducted in compliance with the marketing limitations described in the FDA Code of Federal Regulations (21 CFR §312.7). ICG is FDA approved for routine clinical practice. No return or destruction of study drug is needed for this study.

The pulse dye densitometer (PDD) device used in this study is developed and tested by the Orthopaedics Translational Engineering Lab at DH. It is a modified pulse oximeter which is considered under the abbreviated IDE mechanism (see Section 6.2 for more information).

5.3 Dose Rationale

We plan a sample size of 10 patients in this open label prospective observational study of ICG fluorescence imaging for assessment of subscapularis tendon blood flow.

After the subscapularis tendon is visualized during the surgical approach, 0.1 mg/kg ICG will be injected intravenously. Video rate ICG fluorescence images will be acquired 20 seconds before and 4 minutes after ICG injection. This process will be repeated towards the end of the procedure after the subscapularis is repaired, but prior to skin closure.

This dose has been used to effectively assess bone perfusion in a previous study at our institution which was an IRB-approved pilot study. A total dose of 0.2 mg/kg is within the range of previous studies. Indeed, this is 10 times less than the maximum recommended dose by FDA of 2 mg/kg.

6.0 Procedures Involved*

The research design for this study is a single cohort longitudinal study employing a consecutive sampling methodology. Eligible patients regardless of ethnicity or health

PROTOCOL TITLE: Pilot feasibility study of dynamic contrast-enhanced fluorescence imaging to guide total shoulder arthroplasty approach

status, will be identified and recruited subject to inclusion and exclusion criteria listed in section 10. Patients who meet eligibility criteria will be asked to participate in the trial. If they agree written informed consent will be obtained from the patient or their legal authorized representative. To obtain informed consent, study personnel (surgeon or research coordinator) will adhere to the following procedures: (1) present study information in a manner that is understandable to the patient; (2) discuss the study with the patient and answer any questions; (3) allow the patient an opportunity to discuss participation with their family; (4) confirm that the patient understands the risks and benefits of participating in the study and that their participation is voluntary; (5) complete the consent process and obtain signatures from the patient and research team. The process of obtaining and documenting informed consent forms will be completed in accordance with local Good Clinical Practice (GCP) recommendations.

If the research team member obtaining consent is at all unsure about the patient's ability to consent, s/he will consult with the study PI.

Patients will be randomized to undergo either a subscapularis peel or subscapularis tenotomy.

Recognizing that consent is an ongoing process, the study team will encourage the participants to ask additional questions that may arise during the course of their participation in the study.

On the surgery day, the patient will be prepared and transported to surgery as per routine at Dartmouth-Hitchcock. In the OR, patient positioning, preparation of the surgical field, and draping will follow standard practice for arthroplasty of the involved shoulder joint.

A Pulse dye densometer (PDD; in-house developed), similar to a pulse oximetry probe, which is used clinically both in the operating room, in inpatients as well as outpatients to assess oxygen saturation. This is completely non-invasive. In the context of this study the pulse dye densometer collects data on the ICG injection parameters so that the kinetic curves can be normalized to injection-related differences. The PDD will be placed on the patient's finger to acquire an arterial blood input function during ICG injection.

After the subscapularis tendon is visualized during the surgical approach, 0.1 mg/kg ICG will be injected intravenously. Video rate ICG fluorescence images will be acquired 20 seconds before and 4 minutes after ICG injection. This process will be repeated towards the end of the procedure after the subscapularis is repaired, but prior to skin closure.

ICG will be administered by an anesthetist in the operating room. Patients are under the care and observation of the anesthesia and surgical teams during this time. Postoperatively, patients are transferred to the Post-Anesthesia Care Unit (PACU) where they are monitored

PROTOCOL TITLE: Pilot feasibility study of dynamic contrast-enhanced fluorescence imaging to guide total shoulder arthroplasty approach

continuously by nursing staff supervised by anesthesiologists. During this entire time vital signs (including temperature, pulse, respiratory rate and blood pressure) are collected as standard of care. All clinical data will be reviewed for adverse events for a period of 30 minutes post-injection.

Day of surgery Procedures	Pre-Infusion	0-30 minutes post-infusion
Pulse	X	X
Blood Pressure	X	X
Temperature	X	X
Respiratory Rate	X	X
Adverse Events		X

Study patients will be seen per usual protocol for wound assessment and general health assessment after their shoulder arthroplasty at approximately 4 weeks post operatively.

6.2 Pulse Dye Densitometry Device

A Pulse dye densometer (Pulsion Medical Systems), similar to a pulse oximetry probe, which is used clinically both in the operating room, in inpatients as well as outpatients to assess oxygen saturation. This is completely non-invasive. In the context of this study the pulse dye densometer collects data on the ICG injection parameters so that the kinetic curves can be normalized to injection-related differences. We have a manuscript that was submitted for publication recently demonstrating the importance of collecting this data.

Data obtained as part of this study will not be submitted to or held for inspection by the FDA. The device is a custom device and is not being used to determine safety or effectiveness for commercial distribution.

Exemption Status: The device used is being evaluated on an observational basis. However, it is not exempt due to the fact it introduces energy into the subject. We request an abbreviated IDE under 21 CFR 812, given it is a non-significant risk device.

Description: The device comprises of a single Texas Instruments AFE4490SPO2EVM connected to (1) a Microsoft surface (Windows OS) and a (2) Nihon-KodhenTL-301P finger probe. The TI AFE4490SPO2EVM is an evaluation board with analog front-end that allows control and digitization of detected signal from a pulse oximeter. These devices come with a standard 660nm/900nm pulse oximeter finger probe, however, the Nihon-Kodhen probe (805nm/900nm) is used instead. A custom interface is built to

PROTOCOL TITLE: Pilot feasibility study of dynamic contrast-enhanced fluorescence imaging to guide total shoulder arthroplasty approach

connect the NK probe (circular din connector) with the standard RS-232 connector on the TI board. The light produced by the NK probe is comparable to that of a pulse-oximeter and has a similar safety profile. The emission is well below the ANSI limits for skin exposure.

The IDE is not banned by the FDA, is labeled in accordance with FDA regulations and will not be marketed or promoted. The nature of the risk of the device is minimal. It does not present a potential for serious risk to the health, safety or welfare of the study subject. The device is not of substantial importance in diagnosing, curing, mitigating or treating disease.

7.0 Data and Specimen Banking*

Not applicable

8.0 Sharing of Results with Subjects*

Results will not be shared with subjects or others associated with the subject's medical care.

9.0 Study Timelines*

All patients will participate in the following events shown in the table below. Follow up visits will be conducted during standard postoperative clinical visits or over the phone.

Assessment	Visit 1: Enrollment	Visit 2: Surgery	Visit 3: 1 month
Eligibility Screening	●		
Informed Consent	●		
Collection of Demographic & Shoulder Pathology Data	●		
Collection of Surgical Data (e.g. DCE-FI and AIF)		●	
Collection of Peri-Operative Data (e.g., tHb and S _a O ₂)		●	
Collection of Serious Adverse Events	●	●	●

We anticipate enrolling patients for 4-6 weeks for monitoring of serious adverse events. We anticipate completing preliminary analyses within about 6 months given the relatively small patient sample size and relatively high volume of total shoulder arthroplasty surgeries performed at Dartmouth-Hitchcock.

10.0 Inclusion and Exclusion Criteria*

PROTOCOL TITLE: Pilot feasibility study of dynamic contrast-enhanced fluorescence imaging to guide total shoulder arthroplasty approach

The clinical schedule of the orthopaedic surgeon who is the principal investigator will be reviewed by members of the research team for eligible study participants. Identified patients who meet inclusion criteria for the study will be provided information about the study by the orthopaedic surgeon, or a qualified member of their care team, at the time of their pre-operative clinic visit. Patients who wish to participate in the study will then undergo an informed consent process for the study.

Inclusion criteria:

- a. Participant must be 18 years of age or older
- b. Meet clinical and radiographic parameters necessary to undergo shoulder arthroplasty
- c. Subscapularis tendon intact clinically on exam or via advanced imaging
- d. Subject has the ability to have their shoulder arthroplasty completed using either the tenotomy or peel technique.

Exclusion criteria:

- a. Inability of patient to provide informed consent
- b. Iodine allergy
- c. Subscapularis tendon tear or concern for tear
- d. Incarceration
- e. Pregnant women
- f. Patients less than 18 years of age
- g. Prior deltopectoral approach to the ipsilateral shoulder

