Each subscapularis takedown technique requires repair at the conclusion of the procedure when performing shoulder arthroplasty. Repair is crucial for proper force coupling of the shoulder to keep the humeral head implant centered on the glenoid component (Shields *et al.*, 2017). Takedown is still performed in a reverse total shoulder arthroplasty but repair is not required to maintain stability. Each takedown technique is reliant on either tendon to tendon, tendon to bone, or bone to bone interface for healing. Failure of the subscapularis tendon repair can result in pain, instability, decreased functional outcomes and ultimately the need for revision surgery (Choate *et al.*, 2018). Subscapularis tendon failure can sometimes be asymptomatic, however it can also be symptomatic and present with the aforementioned signs. Subscapularis failure rates may approach 50% in long term studies although symptomatic cases likely occur in less than 1% of total shoulder arthroplasties (Entezari *et al.*, 2020). Due to the devastating impact on patients with symptomatic subscapularis failure, there is interest in investigating which subscapularis takedown technique produces the best outcomes. Prior randomized controlled trials as well as systematic reviews have previously been conducted looking at these different takedown techniques, but demonstrated no statistically significant difference in primary endpoints of subscapularis strength at various time endpoint and no statistically significant difference in patient reported outcomes (Lapner *et al.*, 2020). These prior studies did not evaluate subscapularis perfusion post repair, adequate perfusion is necessary for healing to occur with any subscapularis takedown technique.

The takedown method of the subscapularis has previously been shown to have no statistically significant differences with regards to strength, or patient reported outcomes, however if there was a difference noted in tendon perfusion post repair this may provide rationale to choose one technique over another as improved perfusion may correlate to lower risk of repair failure. As this study aims to monitor subscapularis perfusion pre and post repair, the two techniques that the involve the tendon itself for healing will be utilized, peel and tenotomy.

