4.0 Study Endpoints*

Primary end point:

To assess the technology and its ability to see blood supply in the subscapularis tendon before takedown and after employed repair. The benchmark for this is the rise and fall of fluorescence signal approximately 10-40 seconds after injection. Given our experience in DCE-FI for bone fractures, it will be more or less self-evident whether the DCE-FA signal is sufficient for further analysis.

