5.0 Study Intervention/Investigational Agent

5.1 Description:

This study is neither a drug nor a device trial. Patients will be administered FDA approved ICG through intravenous injection and imaged by a FDA approved surgical fluorescence imaging device (Spy Elite or SPY PHI or Medtronic EleVision) which is 0.5 meter away from the subject. Both ICG fluorescence and the imaging system have been used for routine clinical practice for many years. ICG fluorescence imaging utilizes intravenously injected ICG, which is a fluorescent dye that is FDA-approved for clinical use, illuminated with near-infrared light. The ICG dye is indirectly activated and the dynamic fluorescence due to tendon perfusion can be captured by a video rate imaging system. The subscapularis takedown technique will alternate between tenotomy and peel for every other patient taken to the operating room. There is no reason intraoperatively to choose one technique over the other and therefore this puts

PROTOCOL TITLE: Pilot feasibility study of dynamic contrast-enhanced fluorescence imaging to guide total shoulder arthroplasty approach

the patient at no added risk. If the surgeon feels that neither of these techniques are appropriate for the treatment of the patient then the patient will not be approached for enrollment.

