14.0 Withdrawal of Subjects*

Participants will be removed from the protocol if:

- 1) Concern for subscapularis tendon tear or insufficiency occurs.
- 2) The subject withdraws consent.

PROTOCOL TITLE: Pilot feasibility study of dynamic contrast-enhanced fluorescence imaging to guide total shoulder arthroplasty approach

- 3) The subject has an occurrence of a significant clinical event that precludes proceeding with surgery.
- 4) Imaging cannot be completed for any reason

If a participant is withdrawn from the protocol, the PI will mark the data of this subject as "withdrawn" and will add a detailed explanation about the cause of withdrawal in the database.

For subjects who withdraw after the intraoperative imaging, but prior to their first post operative appointment, we will follow-up to see if they still complete their clinical follow up at the 1-month interval, and provide them an opportunity to report any adverse events. We will acquire their follow up results to include these subjects in the statistical analysis portion that only involves the intraoperative image data and infection status.

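### Should eligibility require a planned subscapularis repair, given that the second imaging run is defined only after repair?

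*Protocol*

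**What the plan says.** Protocol Section 10.0 defines the surgical population in two inclusion criteria. Patients must "Meet clinical and radiographic parameters necessary to undergo shoulder arthroplasty", and "Subject has the ability to have their shoulder arthroplasty completed using either the tenotomy or peel technique". A third criterion requires an intact subscapularis, and a tear or suspected tear is an exclusion. No criterion mentions repair or distinguishes anatomic from reverse implants. The surgeon's judgement before approach, in Section 5.1, also concerns only takedown: if "neither of these techniques are appropriate for the treatment of the patient then the patient will not be approached for enrollment".

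The imaging schedule depends on repair. After describing the first injection, Section 6.0 says: "This process will be repeated towards the end of the procedure after the subscapularis is repaired, but prior to skin closure". Section 5.3 repeats this, and Section 15.0 describes one injection before the repair and one after it. The primary endpoint in Section 4.0 is the technology's "ability to see blood supply in the subscapularis tendon before takedown and after employed repair". The primary research question in Section 2.0 is the change in perfusion after takedown and the repair that follows.

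Section 3.0 makes two statements about repair. The first is general: "Each subscapularis takedown technique requires repair at the conclusion of the procedure when performing shoulder arthroplasty". The second concerns reverse implants: "Takedown is still performed in a reverse total shoulder arthroplasty but repair is not required to maintain stability".

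Section 14.0 removes a participant when "Imaging cannot be completed for any reason", with the reason recorded. It does not say whether that participant is replaced.

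**The concern.** The post-repair image is half of every before-and-after comparison, and screening does not check that a repair is planned. The authors evidently know that anatomic and reverse procedures differ in their need for repair, yet the eligibility criteria do not separate them. Read literally, a reverse case with an intact tendon could qualify, receive the first research injection and a study-assigned takedown technique, and then have no point at which the second run is defined. That participant would probably be removed under the incomplete-imaging item in Section 14.0, with no stated replacement.

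With 10 participants, and about 5 per technique under the alternation in Section 5.1, each lost pair is noticeable. The loss would also be avoidable, because recruitment takes place in clinic from the operating surgeon's own schedule. Nor could an analysis plan repair it afterwards: an image that was never acquired cannot be recovered.

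**Working it through.** **Step 1: does the text leave repair open?** The places that bear on it, side by side:

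| Protocol section | What it implies about repair |
|---|---|
| 2.0, primary question | Repair follows takedown; no condition attached |
| 4.0, primary endpoint | Assessed before takedown and after repair; no condition |
| 5.3 and 6.0, imaging | Second run follows repair; no condition |
| 15.0, risks | Two injections, one on each side of the repair; no condition |
| 3.0, general statement | Repair belongs to every takedown technique |
| 3.0, reverse statement | Repair not needed for one purpose, stability |
| 10.0, eligibility | Silent on repair and implant type |

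The two Section 3.0 statements are compatible. Saying that repair is unnecessary for stability is not saying that it is omitted. Section 3.0 also explains that peel and tenotomy were chosen because healing in both involves the tendon itself, which presupposes a repair. Carried out as written, the procedure therefore gives a post-repair run in all 10 participants.

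**Step 2: what has to happen for a pair to be lost?** A reverse case must be enrolled, and its tendon must then be left unrepaired. The protocol states neither. It does not exclude the first, and it gives no frequency for either.

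**Step 3: how much would a lost pair matter?** There is no figure in the protocol to reproduce: the 10 in Section 12.0 is justified by feasibility, with no power or precision calculation. For illustration, the half-width of a 95% confidence interval for a mean paired change, in units of the SD of that change, is t(0.975, n−1)/√n:

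- n = 10: 2.262/3.162 = 0.715
- n = 9: 2.306/3 = 0.769, which is 7% wider
- n = 8: 2.365/2.828 = 0.836, which is 17% wider
- n = 5 (one technique): 2.776/2.236 = 1.242
- n = 4 (one technique): 3.182/2 = 1.591, which is 28% wider than n = 5

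**Step 4: what if omission were common?** Let q be the share of enrolled patients left unrepaired. This is an assumption; the protocol gives no value. Expected complete pairs are 10(1−q), and the chance that all 10 are complete is (1−q)^10. The chance that both techniques keep at least 4 of 5 pairs is [(1−q)^5 + 5q(1−q)^4]².

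| q (assumed) | Expected pairs | P(all 10 complete) | P(both techniques keep at least 4 of 5) |
|---|---|---|---|
| 0 | 10 | 1.00 | 1.00 |
| 0.1 | 9 | 0.349 | 0.84 |
| 0.2 | 8 | 0.107 | 0.54 |
| 0.3 | 7 | 0.028 | 0.28 |

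These rows show sensitivity to q. They are no evidence that q is above zero, and the procedures as written correspond to the first row.

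**The case for a change.** The strongest argument for a change is that procedures written as though everyone is repaired do not secure a repair; they merely assume it. The general statement on repair sits in the Background, is not an eligibility rule, and is followed by a qualification for reverse implants. Eligibility and withdrawal belong in the protocol, so a separate analysis plan cannot be relied on to close the gap. The remedy would be cheap: one line selecting patients whose existing surgical plan already includes repair, and one sentence on replacement, at a centre that describes its volume of these operations as relatively high.

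Much of this stands. Section 10.0 is silent on repair, the line would be harmless, and it would make Sections 3.0, 6.0 and 10.0 read more consistently. What does not stand is the step from silence to a defect. Eligibility criteria need not restate each step that the procedures prescribe for every participant. One surgeon, who is the principal investigator, supplies the screening schedule (Section 10.0), and all patients are enrolled by the primary surgeon (Section 12.0). The control that would make the loss preventable at screening also makes it unlikely in the first place. The lack of a replacement sentence applies to every cause of withdrawal and says nothing particular about repair.

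The precision figures also need care. The primary endpoint is whether a rise and fall of signal can be seen about 10 to 40 seconds after injection, and the protocol specifies no confidence interval for a mean change. The 28% comes from very few degrees of freedom and would follow the loss of any pair for any reason.

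**Conclusion.** No change is called for. The observation is accurate: eligibility does not mention a planned repair, and the second run depends on one. But the procedures prescribe repair without condition, the two Background statements do not conflict, and nothing in the protocol shows that any participant would go unrepaired. Followed as written, the plan gives 10 of 10 pairs.

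The demonstrated loss is therefore nil, and the possible loss is of unknown size. Each pair actually lost would cost about 7% in overall precision, or 28% within one technique, if a mean paired change were estimated and the split were 5 and 5. The conclusion rests on reading the imaging sections as describing what is done in every participant, and on the operating surgeon screening accordingly. If reverse cases without repair were in fact to be enrolled, the conclusion would not hold. A line in Section 10.0 noting that repair is already part of the participant's surgical plan would be a reasonable courtesy to readers, but the study does not depend on it.
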